6.4.1 Primary Safety	
6.4.2 Subgroup analyses	
6.4.3 Analyses related to COVID-19	
6.4.4 Vital Signs	
6.4.5 Laboratory parameter	
6.4.6 Biomarker	
6.4.7 Electrocardiograms	
6.4.8 Adverse events	
6.4.9 Pregnancies	
7. Document history and changes in the planned statistical analysis	
8. References	25

AE	Adverse event	
AF	Atrial fibrillation	
ALT	Alanine aminotransferase	
ASA	Acetylsalicylic acid	
AST	Aspartate aminotransferase	
ATC	Anatomical Therapeutic Chemical	
BARC	Bleeding Academic Research Consortium	
CABG	Coronary artery bypass graft	
CEC	Clinical Events Committee	
CI	Confidence interval	
CRF	Case report form	
csHR	Cause-specific hazard ratio	
CV	Cardiovascular	
ECG	Electrocardiogram	
eCRF	Electronic case report form	
EDC	Electronic data capture	
eGFR	Estimated glomerular filtration rate	
EOT	End of treatment	
ET	Early Termination	
F1.2	F1.2 fragment of prothrombin	
FAS	Full Analysis Set	
FXIa	Activated Factor XI	
hsCRP	High-sensitivity C-reactive protein	
IDMC	Independent data monitoring committee	
ISTH	International Society on Thrombosis and Hemostasis	
ITT	Intention-to-treat	
MedDRA	Medical Dictionary for Regulatory Activities	
MI	Myocardial infarction	
NOAC	Non-Vitamin K oral anticoagulant	
NT-proBNP	N-terminal pro B-type Natriuretic Peptide	
PK	Pharmacokinetic(s)	
PT	Preferred term	
SAE	Serious adverse event	
SAF	Safety analysis set	
SAP	Statistical Analysis Plan	
SFU	Safety follow up	
SOC	System organ class	
TAFI	Thrombin-activatable fibrinolysis inhibitor	
TAT	Thrombin antithrombin complex	
TIA	Transient ischemic attack	
TIMI	Thrombolysis in myocardial infarction	
VKA	Vitamin K antagonist	

1. Introduction

This Phase 2 study will explore two doses of BAY 2433334 in order to determine a lower risk for bleeding when compared to apixaban (a NOAC) as well as the dose that is safe and can be used in a Phase 3 study in the same indication.

Current treatment guidelines recommend the use of long-term oral anticoagulant therapy such as VKAs, or NOACs.

Despite a better benefit-risk profile for NOACs when compared to VKAs, patients receiving NOACs continue to have a significant risk for developing strokes, systemic embolism and CV

death. In addition, even though NOACs lead to less intracranial hemorrhage compared to VKAs, there is still a significant risk for major and clinically relevant non-major bleeding.

BAY 2433334, as an oral FXIa inhibitor, is expected to show a benefit in reducing the risk for stroke in patients with AF in Phase 3. At the same time BAY 2433334 is expected to have a low bleeding risk. This is based on the available preclinical data, data from patients with inherited FXI deficiency and first clinical data from 2 Phase 2 proof-of-concept studies in participants undergoing total knee replacement.

BAY 2433334 is therefore an attractive candidate to evaluate as a potential replacement for NOAC therapy in patients with AF.

The SAP is based on the protocol version 1.0 (approved: 25 SEP 2019).

2. Study Objectives

The primary safety objective of the study is to evaluate if the oral FXIa inhibitor BAY 2433334 when compared to apixaban leads to a lower incidence of bleeding in participants with AF.

The primary safety estimand is the ratio of the proportions of the composite of ISTH major and clinically relevant non-major bleeding within 3 months comparing pooled doses of BAY 2433334 and comparator drug apixaban in adult participants with AF who have taken at least one dose of study medication of BAY 2433334 or comparator drug apixaban, while the participant is alive and exposed to study intervention.

There are no primary efficacy objectives for this trial.

Exploratory efficacy and safety objectives are:

- to explore the efficacy of BAY 2433334 compared to apixaban in reducing the risk for cardiovascular events (CV death, MI, stroke, systemic embolism) in participants with atrial fibrillation,
- to explore additional pharmacokinetic and pharmacodynamic parameters, biomarkers and genetics, and
- to further investigate the study intervention (i.e. mode-of-action-related effects and/or safety) and to further investigate pathomechanisms deemed relevant to cardiovascular diseases and associated health problems.

An overview of the objectives and corresponding endpoints is given in Table 2-1.

Table 2-1 Objectives and Endpoints

Objectives	Endpoints
Primary	
 to evaluate that the oral FXIa inhibitor BAY 2433334 when compared to apixaban leads to a lower incidence of bleeding in participants with AF 	 Primary Safety Endpoints composite of ISTH major and clinically relevant non-major bleeding Secondary Safety Endpoints all bleeding ISTH major bleeding ISTH clinically relevant non-major bleeding ISTH minor bleeding Exploratory Safety Endpoints TIMI clinically significant bleeding TIMI major bleeding TIMI minor bleeding TIMI major bleeding BARC bleeding definition type 1, 2, 3, 5 BARC bleeding definition type 2, 3, 5 BARC bleeding definition type 1
 Exploratory to explore the efficacy of BAY 2433334 compared to apixaban in reducing the risk for cardiovascular events (CV death, MI, stroke, systemic embolism) in participants with atrial fibrillation to explore additional pharmacokinetic and pharmacodynamic parameters, biomarkers and genetics to further investigate the study intervention (i.e. mode-of-action-related effects and/or safety) and to further investigate pathomechanisms deemed relevant to cardiovascular diseases and associated health problems 	 Exploratory Efficacy Endpoint composite as well as individual components of CV death, MI, ischemic stroke, systemic embolism all-cause mortality Other Exploratory Endpoints FXIa inhibition, aPTT, D-Dimer Pharmacokinetics Various biomarkers (e.g. diagnostic, safety, pharmacodynamic, monitoring, or potentially predictive biomarkers)

Abbreviations: AF = atrial fibrillation, aPTT = activated partial thromboplastin time, BARC = Bleeding Academic Research Consortium, CV = cardiovascular, ISTH = International Society on Thrombosis and Hemostasis, MI = myocardial infarction, TIMI = Thrombolysis in myocardial infarction

3. Study Design

Study 19765 is a multicenter, randomized, active-comparator controlled, double-blind, double-dummy, parallel group, dose-finding Phase 2 study.

The study population includes participants of 45 years of age or older with AF documented by ECG evidence with:

- CHA₂DS₂-VASc score \geq 2 if male or
- CHA₂DS₂-VASc score \geq 3 if female.
- Indication for treatment with an oral anticoagulant in:

- any participant currently not treated with an oral anticoagulant (e.g. treatment naïve) or alternatively,
- participant on a NOAC in case of at least one bleeding risk feature (history of a prior bleed within the last 12 months requiring medical attention and / or moderate renal dysfunction with eGFR 30-50 ml/min and / or current clinically indicated antiplatelet therapy with acetylsalicylic acid [ASA] ≤ 100 mg).

Stratification will be based on whether participants received a NOAC before study start or were not treated with any oral anticoagulant.

The planned study duration will be 14-16 weeks, consisting of:

- Screening period (visit 1 until visit 2): 2 weeks (participants will be screened and have to be randomized within 2 weeks of screening. If all information is available, a participant can be randomized on the day of screening (visits 1 and 2 are combined).
- Treatment period (from visit 2 through visit 6 [EOT] or visit 6a [ET]): 12 weeks
- Safety follow-up (visit 7 [SFU]): 14 days (+ 7 days) after EOT or ET.

Study visits will take place as visits at the study sites and telephone calls. Visits at the study sites take place at screening and randomization (visit 1 and visit 2), at week 4 (visit 4) and week 12 (i.e. EOT, visit 6).

[figure not shown]
Telephone calls will take place at week 2 (visit 3), week 8 (visit 5), as well as 2 weeks after the EOT visit for participants who will take study intervention until the planned EOT (i.e. SFU, visit 7).

For participants who prematurely discontinue from study intervention, an early termination (ET) visit (visit 6a) will take place as soon as possible as visit at the study sites. Telephone calls take place 14 days after the ET visit (i.e. SFU, visit 7).

The study design is presented in Figure 3-1: Study design overview.

Page: 7 of 25:

Figure 3-1: Study design overview

Duration of Treatment: 12 weeks

Note: Participants receiving BAY 2433334 will also receive the apixaban matching placebo. Participants receiving apixaban will also receive the BAY 2433334 matching placebo. During the safety follow-up, further therapy (e.g. NOAC) is at discretion of the investigator.

4. General Statistical Considerations

4.1 General Principles

The statistical evaluation will be performed by using the software package SAS release 9.4 (SAS Institute Inc., Cary, NC, USA).

All variables will be analyzed by descriptive statistical methods. The number of data available and missing data, mean, standard deviation, minimum, quartiles, median, and maximum will be calculated for metric data. Frequency tables will be generated for categorical data.

Data will be displayed by randomized treatment arm.

Potential pre-specified clinical outcome events will be submitted for adjudication to an independent clinical event committee (CEC). Adjudication of all bleeding events as well as potential exploratory efficacy events will be performed by members of the CEC who will review events in a blinded fashion and will adjudicate and classify the following events in a consistent and unbiased manner according to definitions contained in the CEC charter:

- Bleeding events according to the following classifications:
 - ISTH (major, clinically relevant non-major and minor)
 - TIMI (major, minor, requiring medical attention, minimal)
 - BARC (type 1, 2, 3, 5)
- Death (CV death [including death with unknown cause] or non-CV death)
- MI

- Stroke (ischemic, hemorrhagic, undetermined)
- Systemic embolism

In addition, events that might be indicative of a potential outcome event will be reported as outcome events to ensure that no outcome event is missed. This includes for example TIA and hospitalization for cardiac chest pain and with increased cardiac enzymes reported. Data entry procedures and documentation necessary for case adjudication will also be described in the CEC charter. Adjudication results will be the basis for the final analysis.

4.2 Handling of Dropouts

In some instances, it may be necessary for a participant to permanently discontinue study intervention. If study intervention is definitively discontinued, the participant will remain in the study to be evaluated for bleeding and efficacy outcome events until the planned regular end of treatment. In this study, all efforts must be taken to engage patients to comply with all study procedures and to continue to be followed until the end of the study.

A subject who discontinues study participation prematurely for any reason is defined as a "dropout" if the subject is randomized to study treatment. A subject is regarded a "screening failure" if he or she consented to participate in the study but is not subsequently assigned to study intervention.

In all cases, the reason for withdrawal must be recorded in the electronic case report form (eCRF) and in the subject's medical records.

A participant will be considered lost to follow-up if he or she repeatedly (twice) fails to return for scheduled visits and is unable to be contacted by the study site. A participant may withdrawal of consent at any time. This should only occur in exceptional cases and means that the participant does not agree to any kind of follow-up and specifically refuses any further contact with the investigator. All data collected before withdrawal of consent will be used for analysis.

The number of subjects who prematurely discontinue the study during the treatment phase or during the post-treatment observation phase for any reason, as well as the reasons for premature discontinuation of study, will be displayed by treatment arm. Baseline characteristics will be displayed by premature discontinuation (yes/no) from study. The number of subjects who are considered lost to follow-up during the treatment phase or during the post-treatment observation phase will be displayed by treatment arm.

4.3 Handling of Missing Data

All efforts will be made to collect complete data for all participants randomized in this study. Participants will be followed up to the safety follow-up visit and all required data will be collected.

Data from participants who prematurely discontinue the study will be used to the maximum extent possible. Participants that discontinued from study drug will remain in the study to be evaluated for bleeding and efficacy outcome events until their planned regular end of treatment visit. All missing or partial data will be presented in the participant data listing as they are recorded in the eCRF. Data are collected primarily through an EDC system, which allows ongoing data entry and monitoring.

Additional descriptive analyses in the presence of missing data

All dropouts will be carefully evaluated with respect to

- baseline characteristics,
- potential differences between the treatment groups in the proportion of participants withdrawals or in the timing of withdrawals, and
- the reasons for premature discontinuation of study and/or study treatment, and potential dropout patterns will be described.

General rules

When appropriate, the following rules will be implemented so as not to exclude participant from statistical analyses due to missing or incomplete data:

• Incomplete date of outcome

When only partial dates are available, the following rule will be used for the derivation of dates for efficacy and safety events as well as for the date of Adverse events: Any event will be assumed to happen as early as possible, i.e. the earliest of the timeframe known but not earlier than the last date where the participant is known event free.

• Incomplete time of outcome

For events happening at the day of first study drug intake with no timepoint it will be assumed that they happen after the first intake of study drug, i.e. the time of study drug intake will be used for the time of the outcome.

4.4 Interim Analyses and Data Monitoring

An independent Data Monitoring Committee will review safety data according to the IDMC charter. No alpha adjustment is required. No formal interim analysis is planned. Two non-formal interim analyses are planned, and the statistical analysis will be done by an independent statistical analysis center. A separate SAP will be prepared for this.

4.5 Data Rules

4.5.1 Baseline values

Baseline values for vital sign measures and laboratory values are planned to be taken at Visit 2 before administration of study drug. If these values are not available, values taken before first administration of study drug will be considered (e.g., values taken on Visit 1). In case of more than one available value before first administration of study drug, the non-missing value closest to Visit 2 will be taken.

4.5.2 Data Scopes

Treatment emergent data scope

For the treatment emergent data scope all events from first intake of study drug up until 2 days after the last intake of study treatment will be counted. The time to event for participants with no event until 2 days after the last intake of study drug (end of data scope) will be censored at that day.

For events at the day of randomization will be counted if the time of occurrence is later than the time of first study drug intake.

This data scope will be used to handle intercurrent events according to the "while on treatment" strategy.

Intention-to-treat (ITT) data scope

For the intention-to-treat (ITT) data scope all events from randomization up until end of treatment visit (Visit 6) (end of data scope) will be counted. The time to event for participants with no event up until the end of treatment visit will be censored at that day.

This data scope will be used to handle intercurrent events according to the "treatment policy" strategy.

4.5.3 Time-to-Event variables

For the treatment emergent data scope, the time from first intake of study drug to an event is of interest. The time to an event (in days) will be derived the following:

Date of Event – Date of first study drug intake + 1.

For time to event variables in the intention-to-treat (ITT) data scope the time from randomization to an event is of interest. The time to an event (in days) will be derived the following:

Date of Event – Date of randomization + 1.

Survival functions, incidence rates and cumulative hazard calculations will be done only for endpoints with at least 3 events in at least one treatment arm. (Cause specific) hazard ratios (csHR) will be calculated only if in addition at least 1 event in each of the compared treatment arm occur.

If treatment arms are pooled the number of events needed applies on the pooled arm not on each treatment arm.

4.5.4 Special cases of censoring

In special cases, the censoring differs from the section before.

If no event is observed, the censoring date will be determined by the following:

- In case of death of the participant before visit 6:
 - the date of the death.
- In case the participant dies after the end of treatment visit (visit 6) but before the safety follow-up (visit 7)
 - the censoring date according to the "treatment policy" strategy is the date of visit 6
 - the censoring date according to the "while on treatment" strategy is the earliest of 2 days after last study drug intake and the date of death.
- In case the participant is lost to follow up before end of data scope
 - the last study contact date, defined as the latest date of any visit date and dates of any (outcome) events
 - if the vital status is known alive at any date after the last study contact date: for the event death (including CV and non-CV-death): the date of this information.
- In case the participant withdraws consent before end of data scope
 - the date of withdrawal of informed consent

• if the vital status is known alive at any date after the last study contact date: for the event death (including CV and non CV-death): the date of this information.

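### For participants lost or withdrawn, section 4.5.4 censors the death endpoints at any later known-alive date without a cap at the end of the 12-week scope, which understates the exploratory per-arm death rates

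*SAP*

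**What the plan says.** SAP section 4.5.2 defines the intention-to-treat scope: "all events from randomization up until end of treatment visit (Visit 6) (end of data scope) will be counted". The default censoring follows from it: "The time to event for participants with no event up until the end of treatment visit will be censored at that day". Section 6.2 places the efficacy endpoints, including CV death and all-cause mortality, in this scope for the full analysis set.

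Section 4.5.4 then departs from the default: "In special cases, the censoring differs from the section before". Two of its cases matter here. One begins "In case the participant is lost to follow up before end of data scope", the other "In case the participant withdraws consent before end of data scope". Each has a sub-rule that applies "if the vital status is known alive at any date after the last study contact date: for the event death" (CV and non-CV death included). The censoring date is then the date of that information. Neither sub-rule sets a latest date.

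In the same section, a participant who dies between Visit 6 and the safety follow-up is cut at the scope end: under treatment policy the censoring "strategy is the date of visit 6". The on-treatment rule in that bullet takes the earlier of two dates.

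Section 6.2 computes each arm's incidence rate as participants with an event divided by summed time to event or censoring, per 100 participant-years, with a 90% confidence interval.

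**The concern.** A rate is coherent only if numerator and denominator cover the same window. For a completer both stop at Visit 6, even if that person is known to be alive, or known to have died, later. For a participant lost or withdrawn and later found alive, the denominator runs on to whatever date that information carries. Someone lost at day 30 and found alive at day 200 contributes 200 days, against about 85 for a completer.

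The extra time is event-free by construction, since it is added only for people known to be alive. If deaths after the scope are not counted, the rate can only move down. A second gap sits beside this one. Section 4.5.2 ends the scope at a visit that a lost or withdrawn participant may never have, so the SAP does not settle whether a late death in such a participant counts.

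At stake are the exploratory per-arm incidence rates for all-cause and CV death and their confidence intervals.

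**Working it through.** The SAP states no figure on this point, so there is nothing to reproduce. The check applies the section 6.2 formula with and without a cap.

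**Inputs from the SAP**
- Scope end: week 12, which section 6.4.1.2 gives as day 85.
- Safety follow-up: 14 days (+7) after end of treatment (section 3), so at the latest about day 85 + 21 = 106.
- Rate: 36,525 × events / summed days (section 6.2).

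**Assumptions, not in the SAP**
- 250 participants per arm, and 3 deaths in scope at mean day 42.
- A share *s* of the arm is lost or withdrawn and later known alive at day *L*.

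**Capped rate.** Everyone without an event contributes 85 days: 247 × 85 + 3 × 42 = 21,121 days. Rate = 3 × 36,525 / 21,121 = 5.19 per 100 participant-years.

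**Uncapped rate.** Added days = 250 × *s* × (*L* − 85). For *s* = 5% and *L* = 365: 12.5 × 280 = 3,500 days. Rate = 3 × 36,525 / 24,621 = 4.45. Ratio to the capped rate = 21,121 / 24,621 = 0.858.

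| Share later known alive | Day 106 | Day 180 | Day 365 |
|---|---|---|---|
| 2% | 5.16 (0.995) | 5.07 (0.978) | 4.87 (0.938) |
| 5% | 5.12 (0.988) | 4.91 (0.947) | 4.45 (0.858) |
| 10% | 5.06 (0.976) | 4.66 (0.899) | 3.90 (0.751) |

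Cells show the uncapped rate and, in brackets, its ratio to 5.19. Near safety follow-up the understatement is at most 2.4%, even at 10%. At 5% and day 365 it is 14.2%.

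**Confidence limits.** The limits in section 6.2 are the rate times chi-square factors that depend only on the number of events. They shrink by the same ratio.

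**Other planned summaries.** Nelson-Aalen increments and Cox partial-likelihood terms arise only at event times. Up to day 85 the participant is in the risk set whether censored at day 85 or later, and with no counted event after that the extra time adds nothing. A simulated data set (2,000 participants, 8% known alive at day 365, only in-scope deaths counted) agrees. The day-85 risk was 0.045 and the log hazard ratio 0.155 under both rules, while the incidence rate fell from 19.7 to 15.7 per 100 participant-years. Crude percentages do not use censoring time.

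**The case against.** The strongest reply is that a limit is implied. Both sub-rules are triggered by loss or withdrawal before the scope ends, sections 4.2 and 4.3 follow participants to the planned end of treatment, and the rule usefully keeps known-alive information from within the 12 weeks. That purpose is sound, but the implied limit does not follow. The trigger decides who enters the rule, not which date comes out. The section states that it departs from the general censoring, and it writes limits explicitly in the neighbouring bullet.

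The reply on size mostly stands. Section 3 plans 14 to 16 weeks in all, and no survival check at day 180 or 365 is described. Section 4.2 treats withdrawal of consent as exceptional. The case closest to the document is therefore day 106, with an effect below 3%. The later dates are illustrations only.

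Two stronger readings are tempting. A reader might infer that the Aalen-Johansen curves and hazard ratios are distorted because only dropouts known alive remain at risk after day 85. With only in-scope deaths counted, they are not. A reader might also infer that unequal dropout biases the comparison of arms. Section 6.2 plans no rate ratio or rate difference. Its comparisons are Gray's test and cause-specific hazard ratios, which are essentially unchanged; Visit 6 dates slightly after day 85 could have at most a trivial effect.

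**Conclusion.** Wrong as written, minor severity. Followed literally, section 4.5.4 adds out-of-scope event-free time to the denominator of the all-cause and CV death rates and lowers those per-arm rates and their confidence limits. The size rests on assumptions: below 3% with known-alive dates near safety follow-up, about 14% with 5% of an arm known alive at day 365.

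The reach is narrow. Efficacy is exploratory, section 4.5.3 computes rates only for endpoints with at least 3 events in at least one arm, and the rule covers the event death only. The primary bleeding endpoint is not touched. That the other mortality summaries are safe depends on deaths after the scope not being counted, which the SAP leaves open for participants without a Visit 6.

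**What to change.** In both vital-status sub-rules of section 4.5.4, censor the death endpoints at the earlier of the known-alive date and the planned end of treatment (planned Visit 6 date, randomisation + 12 weeks). Apply the same limit to counting deaths in participants who have no Visit 6, so that numerator and denominator share one window.

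The cost is two amended lines plus one sentence in the SAP, and one minimum function in the derivation. No information from within the 12 weeks is lost.
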